7.3. Clinical Laboratory Evaluations

7.3.1. Laboratory Parameters

Clinical laboratory tests include hematology, blood chemistry, urinalysis, myocardial enzymes, coagulation, thyroid function test for Parts 1 and 2 and virology (screening only). Clinical laboratory tests will be measured according to Schedule of Study Assessments in protocol.

Laboratory data from all local laboratories will be included in the analyses. The default convention for reporting of laboratory units will be standard international (SI) units. If a lab value is reported using an inequality symbol e.g., less than (<) a certain value, or greater than (>) a certain value, the given numeric value will be used in the summary. Data will be presented in listings with their inequality symbol.

All lab results will be graded by the low/normal/high classifications based on each specific laboratory normal reference ranges. All applicable lab results will be graded to toxicity grades according to NCI CTCAE v5.0 when possible. Both scheduled and unscheduled during on-treatment period assessments will be used to identify the maximum post-baseline toxicity grade. Any laboratory parameter for which CTCAE toxicity grades’ criteria include clinical inputs will be graded based on numerical criteria.

For continuous parameters, changes from baselines in hematology, blood chemistry, myocardial enzymes, coagulation, and thyroid function tests will be calculated. The maximum and minimum post-baseline will be derived over the entire on-treatment post-baseline period. Urinalysis data will be categorized as negative (0), positive (+), or strongly positive (++ , +++ , or >+++) at each timepoint.

For the liver function tests AST, ALT, ALP, total bilirubin (TBL), the fold of the local lab upper limit of the normal (ULN) range will be calculated for each data point as $\text{Fold} = \text{Value} / \text{ULN}$.

7.3.2. Laboratory Data Summary

All laboratory data will be included in the analyses. The default convention for reporting of laboratory units will be standard international (SI) units. If a lab value is reported using an inequality symbol e.g., less than (<) a certain value, or greater than (>) a certain value, the given numeric value will be used in the summary.

In general, summaries will include all laboratory assessments during the on-treatment period. The minimum and maximum values and their corresponding change from baseline for each

Statistical Analysis Plan for Protocol ABSK-021-301

patient over the entire treatment period for each hematology and chemistry laboratory parameter will also be derived.

Observed values and changes from baseline from continuous laboratory parameters will be summarized by treatment groups for each scheduled analysis visit, overall maximum and minimum post-baseline during the on-treatment period. If a patient has multiple laboratory assessments in an interval of interest, the maximum CTCAE grade will be reported.

Shift summaries in CTCAE grade from baseline to the worst post-baseline value by treatment groups will be produced for selected laboratory parameters, including at least hemoglobin, WBC count, ANC, absolute lymphocyte count, platelet count, AST, ALT, bilirubin, creatinine, alkaline phosphatase, INR, PTT, amylase, CK, lipase, and electrolytes (bi-directional) for overall on-treatment period. The shift tables will present baseline and worst post-baseline value (for bi-directional laboratory tests, summarization will be according to specified direction), as applicable for each parameter and will include patients with both baseline and at least one post-baseline data. Any assessment for which CTCAE toxicity grades are not available, will not be included in any analyses for which toxicity grades are required. Instead, these parameter results will be graded by clinically significant results based on the investigators judgements.

Laboratory parameters graded by NCI CTCAE will be summarized using shift tables. The number and percentage of patients graded according to CTCAE v5.0 will be presented as shift table of:

- Patients with Baseline versus their worst post-Baseline grade (for bi-directional laboratory tests, summarization will be according to specified direction)

Any graded abnormality that occurs following the initiation of the study drug and represents at least a 1-grade increase from the baseline assessment is defined as a treatment-emergent abnormality. Patients with laboratory treatment-emergent abnormality in CTCAE grade will be summarized for all grades and grade 3 or 4. Subgroup analyses will also be performed.

Time to the first onset of laboratory treatment-emergent abnormality in CTCAE will be summarized descriptively.

To evaluate the status of missing data, for AST, ALT, alkaline phosphatase, total bilirubin, gamma-glutamyl transferase, international normalized ratio and creatinine, the figures of proportion of patients remaining with missing and existing laboratory data records will be provided. The figures evaluate the actual data obtained during the trial rather than the planned study procedures as stated in the protocol.

For hepatotoxicity screening, the following categories of abnormal hepatic laboratory values will be summarized by treatment group for any occurrence among all on-treatment period assessments, including scheduled and unscheduled values.

- Criterion 1: ALT and/or AST $\geq 3xULN$, ALP $< 2xULN$ or missing, and Total Bilirubin $\geq 2xULN$
- Criterion 2: ALT and/or AST $\geq 3xULN$, and total bilirubin $\geq 2xULN$
- Criterion 3: ALT and/or AST $\geq 3xULN$, ALP $< 2xULN$, and total bilirubin $\geq 1.5xULN$
- Criterion 4: ALT $\geq 3xULN$ and ALP or Gamma-glutamyl Transferase (GGT) $\geq 2xULN$ and TBL $\geq 2xULN$
- Criterion 5: ALP or GGT $\geq 2xULN$ and TBL $\geq 2xULN$

Statistical Analysis Plan for Protocol ABSK-021-301

For these categories, patients are counted as having any post-baseline total bilirubin equal to or exceeding 2xULN or 1.5xULN within 15 days after a post-baseline ALT or AST equal to or exceeding 3xULN, and ALP <2xULN or not. Or within 15 days after a post-baseline ALP or GGT equal to or exceeding 2xULN, and ALT \geq 3xULN or not.

The eDish plot is intended to quickly identify cases of possible serious hepatocellular DILI, each patient is plotted based on their maximum post-baseline total bilirubin and transaminase (ALT or AST, whichever is higher). Each value is expressed as multiples of ULN on logarithmic scales. Dashed lines in this plot represent total bilirubin and transaminase cutoffs of 2xULN and 3xULN, respectively and are based on the criterion 1 above.

A line plot of liver function tests, including ALT, AST, ALP and total bilirubin, over time will also be presented for each individual patient who meet the criterion 1 above.

In addition, the following categories of liver function abnormality levels will be derived and summarized by treatment groups. No subgroup analysis will be conducted.

- For ALT, AST, ALT and/or AST: ≥ 3 and $< 5 \times \text{ULN}$, ≥ 5 and $< 10 \times \text{ULN}$, $\geq 10 \times \text{ULN}$, $\geq 20 \times \text{ULN}$
- Total bilirubin: ≥ 1.5 and $< 2 \times \text{ULN}$, ≥ 2 and $< 3 \times \text{ULN}$, $\geq 3 \times \text{ULN}$
- ALP: ≥ 1.5 and $< 2 \times \text{ULN}$, ≥ 2 and $< 3 \times \text{ULN}$, $\geq 3 \times \text{ULN}$

And renal function abnormality levels will be summarized following the categories:

- Creatinine: ≥ 1.5 and $< 2 \times \text{baseline}$, ≥ 2 and $< 3 \times \text{baseline}$, $\geq 3 \times \text{baseline}$
- eGFR change from baseline: $\geq 25\%$ and $< 50\%$ decrease, $\geq 50\%$ and $< 75\%$ decrease, $\geq 75\%$ decrease

All laboratory results will be listed with values flagged to show the corresponding CTCAE grades and the classifications relative to the laboratory reference ranges. In addition, a separate listing will be prepared for patients who met the criterion 1.

7.4. Vital Signs

7.4.1. Vital Sign Parameters

Vital signs including pulse rate, respiration rate, body temperature, systolic blood pressure (SBP), diastolic blood pressure (DBP); weight and height will be measured according to Schedule of Study Assessments in the protocol.

Change from baseline for each parameter will be derived. The potentially clinically significant findings of vital signs and weight will be defined based on criteria in [Table 7.1](#). Both scheduled and unscheduled assessments will be used to identify the worst post-baseline values.

Table 7.1 Potentially Clinically Significant Criteria for Vital Signs and Weight

Vital Sign Parameter	Potentially Clinically Significant Criteria	
	Value Categories	Change from Baseline Categories

Statistical Analysis Plan for Protocol ABSK-021-301

SBP	≥ 120 mmHg	Increase ≥ 40 mmHg
	≥ 140 mmHg	Decrease ≥ 40 mmHg
	≥ 160 mmHg	
	≥ 180 mmHg	
	< 90 mmHg	
	≥ 120 mmHg and increase from baseline ≥ 20 mmHg	
DBP	> 90 mmHg	Increase ≥ 20 mmHg
	> 110 mmHg	Decrease ≥ 40 mmHg
	≥ 120 mmHg	
	≤ 60 mmHg	
	≥ 80 mmHg and increase from baseline ≥ 20 mmHg	
Pulse Rate	≥ 110 bpm	Increase ≥ 40 bpm
	≤ 50 bpm	Decrease ≥ 40 bpm
	≥ 120 bpm and increase from baseline ≥ 15 bpm	
	≤ 50 bpm and increase from baseline ≥ 15 bpm	
Weight	n/a	Increase $\geq 10\%$
		Decrease $\geq 10\%$
Respiratory Rate	> 20 breaths/min	
	< 12 breaths/min	

Note: bpm = beats per minute

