4.2.2.3. Baseline and Change from Baseline

For patients who were randomized to ABSK021 group at the beginning of trial, the last non-missing value or mean on or before the randomization will be used as a baseline for efficacy endpoints, while the last recorded value on or before the first Part 1 dose of study drug will serve as the baseline measurement for safety endpoints unless it is specified stated otherwise. If multiple planned assessments are collected on the same scheduled time, the average of these assessments will be used.

For patients who were given placebo treatment during Part 1 of the study and then switched to ABSK021 treatment in Part 2, their baseline values for both efficacy and safety parameters at Part 2 will be reassigned based on the non-missing values or means before they were given their first Part 2 dose. Baselines at Part 1 will follow the same rule described for patients who were randomized to ABSK021 group.

Statistical Analysis Plan for Protocol ABSK-021-301

Absolute changes from baseline will be calculated as the post-baseline value minus the baseline value. Percentage changes from baseline will be calculated as the change from baseline divided by the baseline value, multiplied by 100. If either of values is missing, then change from baseline and percentage change from baseline will be set to missing.

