7.4.2. Vital Sign Summary

The summaries will include all vital sign data collected during the on-treatment period. Observed values and changes from baseline for each vital sign parameter will be summarized by treatment groups ([Section 7.1](#)) for each scheduled analysis visit, overall maximum and minimum post-baseline during on-treatment period.

Statistical Analysis Plan for Protocol ABSK-021-301

The number and percentage of patients who met any potentially clinically significant criteria for each vital sign parameter as described in [Table 7.1](#) will be summarized by treatment groups for the overall on-treatment period.

All observed vital sign values and change from baseline with the abnormality flag will be listed.

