7.5. ECG Data

7.5.1. ECG Parameters

The standard 12-lead ECG value for heart rate, PR interval, RR interval, QRS interval, QT, QTcF, and investigator's clinical interpretation of 12-lead ECG (normal or abnormal) will be collected according to Schedule and Assessment Table in the protocol.

QTcF values collected on CRF page will not be used for analysis, instead, derived QTc values will be the basis for reporting. Corrected QTcF and QTcB will be calculated as follows from uncorrected QT and RR (converted from collected msec to sec) as follows:

$$\text{Bazett's method QTcB} = \text{Uncorrected QT} / (\text{RR Interval})^{1/2}$$

$$\text{Fridericia's method QTcF} = \text{Uncorrected QT} / (\text{RR Interval})^{1/3}$$

Change from baseline in each ECG parameter will be derived. ECG potentially clinically significant criteria are listed in [Table 7.2](#) below. Both scheduled and unscheduled assessments will be used to identify the worst post-baseline values.

Table 7.2 Potentially Clinically Significant Criteria for ECG Parameters

ECG Parameter	Potentially Clinically Significant Criteria	
	Value Categories	Change from Baseline Categories
Heart Rate	>120 beats/min	n/a
	>120 beats/min and change from baseline > 25% increase	
	<50 beats/min	n/a
	<50 beats/min and change from baseline > 25% decrease	
RR Interval	>1200 msec	n/a
	<500 msec	n/a
PR Interval	≥ 210 msec	n/a
	≥ 210 msec and change from baseline > 25% increase	
QRS	≥ 120 msec	n/a

Statistical Analysis Plan for Protocol ABSK-021-301

ECG Parameter	Potentially Clinically Significant Criteria	
	Value Categories	Change from Baseline Categories
	≥ 120 msec and change from baseline $> 25\%$ increase	
	≤ 50 msec	n/a
QT Interval	≥ 500 msec	n/a
	≤ 300 msec	n/a
Calculated QTcB & QTcF Intervals	≥ 500 msec	Increase ≥ 30 msec
	≥ 480 and < 500 msec	Increase ≥ 30 and < 60 msec
	≥ 450 and < 480 msec	Increase ≥ 60 msec
	≤ 300 msec	
	≥ 500 msec and increase from baseline ≥ 60 msec	

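### In SAP Table 7.1 the combined low-pulse row has its direction of change reversed, so it cannot count a pulse that fell to 50 bpm or below

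*SAP*

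**What the plan says.** SAP 7.4.1, Table 7.1, gives pulse rate four value categories and two change-from-baseline categories.

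- **High values:** 110 bpm or more, and the combined row "≥ 120 bpm and increase from baseline ≥ 15 bpm".
- **Low values:** 50 bpm or less, and the combined row "≤ 50 bpm and increase from baseline ≥ 15 bpm".
- **Change alone:** a rise of at least 40 bpm, and a fall of at least 40 bpm. The fall is printed on the same line as the stand-alone low value ("≤ 50 bpm Decrease ≥ 40 bpm"), but the two sit in different columns and are separate categories.

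The sign of a change is fixed in SAP 4.2.2.3: "Absolute changes from baseline will be calculated as the post-baseline value minus the baseline value". SAP 7.4.2 puts the table to use: "The number and percentage of patients who met any potentially clinically significant criteria for each vital sign parameter" are summarised by treatment group for the on-treatment period.

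The counterpart for ECG heart rate, in SAP 7.5.1, Table 7.2, is "<50 beats/min and change from baseline > 25% decrease". Protocol 7.4.7.2 leaves the criteria for vital signs and ECG to the SAP, so no other text corrects the pulse row.

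**The concern.** A row that combines a value with a change is there to separate a new abnormality from a patient's usual level. For low pulse, that means separating someone whose pulse has dropped on treatment from someone whose pulse is always low. The row as written asks for a rise, so it selects neither.

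The rule will be programmed for a by-group count. SAP Table 4.7 defines five safety display groups and repeats them across the planned analyses, so the same row will recur. A row of zeros could be read as reassurance when it only reflects a condition that almost nobody can meet. A programmer who notices must either follow the text or correct it without authority. SAP section 1 asks for deviations from the plan to be justified and documented in the study report.

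**Working it through.** The plan states no figure to reproduce here. The check is algebra on the row, a count over possible values, and a comparison with the other combined rows.

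**1. Who can meet the row.** Let B be baseline and P the post-baseline pulse, with change = P − B (SAP 4.2.2.3). The row requires P ≤ 50 and P − B ≥ 15. Hence B ≤ P − 15 ≤ 50 − 15 = 35 bpm. A change from 35 to 50 bpm qualifies. No fall of any size does.

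**2. Count over a grid.** Take all whole-number pairs with B and P from 20 to 140 bpm. New low pulse is taken as B > 50 and P ≤ 50. This is an assumption, because the SAP does not define the term for pulse; 50 bpm is the table's own cut-off. That gives 90 baselines (51 to 140) × 31 post-baseline values (20 to 50) = 2,790 pairs.

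| Table 7.1 pulse category | Pairs flagged, of 2,790 |
|---|---|
| Combined low row, as written | 0 |
| Combined low row, with a decrease | 2,685 |
| 50 bpm or less, stand-alone | 2,790 |
| Fall of 40 bpm or more | 2,046 |

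These are counts of grid points, not patient rates. The 105 pairs that the corrected row leaves out (2,790 − 2,685) are falls of less than 15 bpm.

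**3. Examples.**

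| Baseline → post | Row as written | Row with a decrease | 50 or less alone | Fall of 40 or more | ECG combined row, if ECG rate equals pulse |
|---|---|---|---|---|---|
| 70 → 48 | no | yes | yes | no | yes (fall 22/70 = 31%) |
| 66 → 50 | no | yes | yes | no | no (not below 50; fall 16/66 = 24%) |
| 90 → 50 | no | yes | yes | yes | no (not below 50) |
| 35 → 50 | yes | no | yes | no | no |

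**4. Comparison with the other combined rows.** Tables 7.1 and 7.2 hold nine rows that pair a value with a change: systolic pressure, diastolic pressure, high pulse and low pulse in Table 7.1; high heart rate, low heart rate, PR, QRS and QTc in Table 7.2. Eight pair a high value with a rise or a low value with a fall. Low pulse is the only exception, and it repeats the direction and size of change of the high-pulse row directly above it. That pattern fits a drafting slip rather than a deliberate criterion.

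**The case against.** The strongest reply is that little information is lost, and most of that reply stands.

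- The stand-alone category of 50 bpm or less flags every patient who reaches that level, including every new case.
- The ECG combined row is a close substitute. In Part 1, vital signs and ECG are scheduled at the same visits (Protocol Table 1), and SAP Table 4.3 gives them the same windows. If ECG rate tracks pulse, the baselines required are similar. At 49 bpm the corrected pulse row needs at least 64, and the ECG row needs more than 49/0.75 = 65.3. At 45 bpm the figures are at least 60 and more than 60. At 40 bpm they are at least 55 and more than 53.3.
- SAP 7.4.2 also summarises changes by visit and the overall minimum post-baseline value, and lists all values and changes with an abnormality flag. Clinically significant vital-sign abnormalities are adverse events under Protocol 8.1.1.1.
- SAP 7.1 generally plans no inferential testing of safety data, and SAP Appendix 4 has no bradycardia category.

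A reader might infer from the faulty row that treatment-emergent bradycardia would go unseen, or that the study report would show none whatever happened. The outputs listed above rule that out.

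The reply does not make the row right. The stand-alone category ignores baseline, so it mixes habitually low pulses with new ones. The category for falls of 40 bpm or more needs a baseline of at least 90 to flag a pulse that ends at 50. The ECG row is a different measurement, with a strict cut-off below 50 and a relative fall.

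**Conclusion.** The combined low-pulse row is wrong as written. It can be met only from a baseline of 35 bpm or less, by a pulse that rose, and it cannot count a pulse that fell to 50 bpm or below. The loss is one category: a low pulse together with a moderate fall. The effect is confined to descriptive safety tables; no efficacy, estimand or multiplicity result depends on it.

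The algebra assumes that both conditions apply to the same assessment, which is the natural reading of the row. That the row will be essentially empty rests on baselines of 35 bpm or less being very rare. This is plausible, but it is an assumption. A reader might go further and expect exactly none of the roughly 90 planned patients, but the documents give no baseline pulse data to support a definite count.

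**What to change.** In SAP Table 7.1, replace the word *increase* with *decrease* in the combined low-pulse row and keep both thresholds. The row then asks for a pulse of 50 bpm or less together with a decrease from baseline of at least 15 bpm, which agrees in direction with the low heart-rate row in Table 7.2. Make the same change in the table shell and the programming specification.

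The cost is one word in each place. It needs no new data and changes no patient-management rule. It should be done before database lock. If lock has already passed, the corrected row should be reported with the reason documented in the study report, as SAP section 1 requires.

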7.4.2. Vital Sign Summary

The summaries will include all vital sign data collected during the on-treatment period. Observed values and changes from baseline for each vital sign parameter will be summarized by treatment groups ([Section 7.1](#)) for each scheduled analysis visit, overall maximum and minimum post-baseline during on-treatment period.

Statistical Analysis Plan for Protocol ABSK-021-301

The number and percentage of patients who met any potentially clinically significant criteria for each vital sign parameter as described in [Table 7.1](#) will be summarized by treatment groups for the overall on-treatment period.

All observed vital sign values and change from baseline with the abnormality flag will be listed.

7.5. ECG Data

7.5.1. ECG Parameters

The standard 12-lead ECG value for heart rate, PR interval, RR interval, QRS interval, QT, QTcF, and investigator's clinical interpretation of 12-lead ECG (normal or abnormal) will be collected according to Schedule and Assessment Table in the protocol.

QTcF values collected on CRF page will not be used for analysis, instead, derived QTc values will be the basis for reporting. Corrected QTcF and QTcB will be calculated as follows from uncorrected QT and RR (converted from collected msec to sec) as follows:

$$\text{Bazett's method QTcB} = \text{Uncorrected QT} / (\text{RR Interval})^{1/2}$$

$$\text{Fridericia's method QTcF} = \text{Uncorrected QT} / (\text{RR Interval})^{1/3}$$

Change from baseline in each ECG parameter will be derived. ECG potentially clinically significant criteria are listed in [Table 7.2](#) below. Both scheduled and unscheduled assessments will be used to identify the worst post-baseline values.

Table 7.2 Potentially Clinically Significant Criteria for ECG Parameters

ECG Parameter	Potentially Clinically Significant Criteria	
	Value Categories	Change from Baseline Categories
Heart Rate	>120 beats/min	n/a
	>120 beats/min and change from baseline > 25% increase	
	<50 beats/min	n/a
	<50 beats/min and change from baseline > 25% decrease	
RR Interval	>1200 msec	n/a
	<500 msec	n/a
PR Interval	≥ 210 msec	n/a
	≥ 210 msec and change from baseline > 25% increase	
QRS	≥ 120 msec	n/a

Statistical Analysis Plan for Protocol ABSK-021-301

ECG Parameter	Potentially Clinically Significant Criteria	
	Value Categories	Change from Baseline Categories
	≥ 120 msec and change from baseline $> 25\%$ increase	
	≤ 50 msec	n/a
QT Interval	≥ 500 msec	n/a
	≤ 300 msec	n/a
Calculated QTcB & QTcF Intervals	≥ 500 msec	Increase ≥ 30 msec
	≥ 480 and < 500 msec	Increase ≥ 30 and < 60 msec
	≥ 450 and < 480 msec	Increase ≥ 60 msec
	≤ 300 msec	
	≥ 500 msec and increase from baseline ≥ 60 msec	

7.5.2. ECG Summary

The summaries will include ECG heart rate, PR interval, RR interval and QT collected from CRF and derived QTcB and QTcF during the on-treatment period.

Observed values and changes from baseline for each ECG parameter will be summarized by treatment groups ([Section 7.1](#)) for each scheduled analysis visit, overall maximum and minimum post-baseline during on-treatment period.

The number and percentage of patients who met any potentially clinically significant criteria for each ECG parameter as described in section above will be summarized by treatment groups for the overall treatment period.

A shift table will be produced to display investigator's clinical interpretation of the 12-lead ECG normal, abnormal – not clinically significant, abnormal – clinically significant and not done. The shift tables will present baseline and worst post-baseline observation including unscheduled values during the overall treatment period.

All ECG parameters ECG heart rate, PR interval, RR interval and QT collected from CRF and derived QTcB and QTcF and change from baseline with the abnormality flags along with investigator's clinical interpretation will be listed.

Statistical Analysis Plan for Protocol ABSK-021-301

